Study Design	Single-center, randomized, single blinded, positive-controlled dose escalation pilot study. Patients receive standard monitoring for anesthesia and postoperative care. Surgical and anesthesia care (except for intraoperative opioid use) are not altered for study purposes. In each cohort, subjects are randomized 1:2 to either control (standard intraop opioid at anesthesiologists' discretion, not methadone) or methadone HCl (0.1 – 0.3 mg/kg ideal body weight, IBW). Subjects in Group I will receive methadone (IV bolus, at induction of anesthesia) as their primary intraoperative opioid. Dose of methadone may be increased up to 0.3 mg/kg IBW following preliminary analysis and review of initial subjects enrolled to Group I. Subjects in Group II (control) will receive intraoperative opioid administration at the discretion of the anesthesia providers (typically fentanyl or morphine). Postoperative pain management for both groups will be per standard of care.
Inclusion and Exclusion Criteria	
Inclusion Criteria
 
 1. Age 18-65 years 2. Undergoing general anesthesia and moderately painful, ambulatory surgical procedures, with anticipated postop stay of < 24 hours 3. Signed, written, informed consent 
Exclusion Criteria
 
 1. History of liver or kidney disease. 2. Females who are pregnant or nursing. 3. Opioid tolerant patients (e.g. preoperative methadone therapy or use of fentanyl transdermal patches) 4. History of allergy to methadone

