Measurements	Total intraoperative and postoperative opioid administration during hospitalization will be recorded from the patient's electronic medical record (EMR). Pain intensity will be assessed using the Numeric Rating Scale (NRS) and colored-visual analogue scale. Pain relief will be assessed using five point scale (0-no relief, 4-complete pain relief). Postoperative sedation will be recorded using Modified Observer's Assessment of Alertness/Sedation (MOAA/S). Assessment of opioid side effects will be performed using Opioid-Related Symptom Distress Scale (ORSDS). Daily opioid consumption and daily pain self-assessments using a colored-visual analogue scale will be recorded in a home diary for approx 30 days following surgery (from hospital discharge until postop clinic visit). Additional ORSDS assessments will be recorded at various timepoints (approx 7, 14 and 30 days postop) in the home diary. Subjects may have their CYP2B6 genotype determined.

Statistical Methodology	Demographic data including race, sex, and age will be analyzed using chi-square and t- test or ANOVA, as appropriate. Baseline characteristics of the cohort will be described. Total daily opioid consumption and pain scores using NRS, will be compared between the groups. Outcome measures will be expressed as the mean and standard deviation. Group outcomes will be compared across the two groups, using t-test and/or analysis of variance, ANOVA and MANCOVA to account for potential cofounders.
Outcomes	
Primary: Intraoperative and postoperative opioid utilization
 
Secondary:
 
 1) Opioid consumption and pain relief within first 30 postoperative days 2) Pain scores and pain self-assessments 3) Influence of CYP2B6*6 genotype on methadone clinical effectiveness for pain relief and opioid consumption

1. Specific Aims

- 1.1. To study the effects of a single dose of methadone on postoperative pain and opioid consumption in patients undergoing moderately painful, ambulatory surgical procedures.
- 1.2. Determine opioid consumption and pain relief within first 30 postoperative days
- 1.3. Determine cytochrome P4502B6 (CYP2B6) genotype in patients receiving methadone, and any relationship to postop pain relief and opioid consumption

2. Background

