We propose to evaluate intraoperative and postoperative opioid consumption, pain intensity and pain relief in patients undergoing moderately painful, ambulatory surgical procedures (anticipated length of stay <24 hrs) in 2 cohorts, and 2 groups in each cohort. Cohort 1 is ambulatory patients with <24 hr overnight stay, cohort 2 is same-day surgery outpatients). In each cohort, Group I will receive a single dose of methadone during surgery and Group II will receive a non-methadone intraoperative opioid (typically fentanyl or morphine). Secondly, we will study opioid consumption and pain self-assessments within approximately the first 30 postoperative days, or until the initial postop clinic visit.

3. Drug Information

Methadone hydrochloride is a synthetic μ -agonist with multiple actions qualitatively similar to those of morphine. Onset of effect is about 2-10 min for parenteral dosing. Methadone is primarily metabolized by N-demethylation to an inactive metabolite, 2-ethylidene-1,5-dimethyl-3,3-diphenylpyrrolidene (EDDP). In vivo, CYP2B6 is a major determinant of metabolism to inactive metabolites which are excreted mainly in the urine. The terminal half-life ($T_{1/2}$) in healthy adults averages 24-36 hrs (11, 12).

CONFIDENTIAL: This document is the intellectual property of [name]. Acceptance of this document constitutes the agreement by the recipient that no unpublished information contained herein will be published or disclosed without prior written approval.

The most common side effect of methadone, like other opioids, is sedation, nausea and vomiting. Respiratory depression is the chief hazard associated with methadone, like all opioids.

4. Eligibility

Inclusion Criteria

- Age 18-65 years
- Undergoing general anesthesia and moderately painful, ambulatory surgical procedures with anticipated postop hospital stay of < 24 hours
- Signed, written, informed consent

Exclusion Criteria

- History of or known liver or kidney disease.
- Females who are pregnant or nursing.
- Opioid tolerant patients (e.g. preoperative methadone therapy or use of fentanyl transdermal patches)
- History of allergy to methadone

5. Enrollment

Subjects will be approached prior to surgery in the Center for Preoperative Assessment and Planning or preoperative holding area. Patients will be consented for participation and enrolled in the study by trained study personnel.

6. Methods

Preoperative and Intraoperative Period

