Enrolled subjects will be asked to complete a questionnaire about their current pain and what they anticipate following surgery. Patients will receive standard physiologic monitoring for anesthesia and postoperative care. Subjects within each cohort (n≥60 evaluable, depending on the number of dose levels in each cohort) are randomized 1:2 to receive either control (typical intraop opioid, such as fentanyl or morphine) or methadone HCl (0.1 – 0.3 mg/kg ideal body weight, IBW). It is anticipated that the first ten patients will receive 0.1 mg/kg IV methadone. If patients still have significant post-op opioid requirements, subsequent groups may receive 0.2 mg/kg and then 0.3 mg/kg ideal body weight.

Anesthesia and surgical care will not be altered for the purposes of this investigation, except that subjects in methadone group will receive methadone as their intraoperative opioid, rather than leaving the choice of intraoperative opioid to the anesthesiologist. The control group patients will receive intraoperative analgesia with opioids other than methadone left at the discretion of their anesthesiologist (typically fentanyl or morphine).

Administration of Study Medication

Methadone is administered as an IV bolus at induction of anesthesia. Methadone hydrochloride is available commercially for injection (10 mg/ml). Subjects randomized to the control group will receive typical (non-methadone) opioids. Both groups will receive standard of care postoperative analgesia as determined by the treating physician. Postoperative care is not altered for purposes of this study.

Assessments

Pain assessments at rest (when patient awake) will be conducted in the postoperative period by a trained member of the research team. These will occur after handoff in the Postop Anesthesia Care Unit (PACU) and approx every 15 minutes during first PACU hour, then approx every hour for the next 4 hours and at bedtime. The pain assessments will also be performed at approx 24 hrs or prior to discharge from the hospital, whichever occurs first. Pain intensity will be assessed using the 0-10 Numeric Rating Scale and a colored-visual analogue scale. Pain relief will be assessed using five point scale (0-no relief, 4-complete

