pain relief). Observed sedation (Modified Observer's Assessment of Alertness/Sedation, MOAA/S) and subject's self-assessment of sedation are recorded at the same intervals as pain assessments. Assessment of opioid side effects is performed at approximately 24 hrs or prior to discharge from the hospital using Opioid-Related Symptom Distress Scale (ORSDS). The total amount of other drugs administered during hospitalization for prophylaxis or treatment of opioid side effects will be recorded from the EMR. Daily home opioid usage and pain self-assessments will be recorded in a home diary. The ORSDS assessments will also be completed at various timepoints (approximately 7, 14 and 30 days postop).

Any adverse events are described, recorded and reported according to GCP and IRB regulations.

7. Data Collection and Monitoring.

Opioid Consumption During Hospitalization

The EMR will be used to calculate the amount of morphine or morphine equivalents administered during surgery and until discharge, as well as other drug administration for treatment and/or prophylaxis of possible opioid side effects.

Follow-up Assessments

A home diary will be used to assess daily drug dosing history upon discharge from the hospital until the patient's postop clinic visit at approximately 30 days. Subjects will also record daily pain self-assessments using a colored-visual analogue scale (at rest, with activity and with coughing). The ORSDS will be completed and recorded on approximately the 7th, 14th and 30th day. We will also ask subjects about remaining number of pain medications and their disposal at the 30 day time point.

CYP Genotyping

Approximately 5 ml of blood will be collected from an IV line for CYP2B6 genotyping. Genotyping will be performed at the WUSTL Genome Technology Access Center (GTAC).

Other Measurements

Required baseline measurements that will be obtained from the EMR are age, vital signs, weight, height, and peripheral oxygen saturation by pulse oximetry and are all collected as standard of care.

8. Data and Safety Monitoring Plan.

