In general, the Department of Anesthesiology has developed a specific set of Standard Operating Procedures (SOPs) for clinical research. All individuals working on study are required to read and be totally familiar with and compliant with the SOPs. The SOPs are in part developed from and are compliant with the Institutional guidelines, including those for a) Interactions with the Washington University Human Subjects Review Committee, b) Informed Consent Development and Implementation, c) Subject Recruitment and Screening, d) Subject Management While on Study, e) Adverse Event Reporting. The specific plan for submitting Adverse Event Reports to the IRB is detailed in the SOP for Adverse Event Reporting.

The specific monitoring plan for this investigation is commensurate with the risks, size and complexity of the investigations planned. The potential risks are attributable to the use of methadone. Based on the small size and relatively low risks nature of the protocol, only the PI and CoI are involved in monitoring plan, rather than a full DSMB. These individuals will review the annual summary of adverse events. In addition, they will review all reports of a Serious Adverse Event, or an Unexpected Adverse Event.

9. Statistical Methods

Primary Assessment

Overall opioid (morphine equivalents) consumption for each patient during hospital stay
Absolute pain and sedation scores

CONFIDENTIAL: This document is the intellectual property of [name]. Acceptance of this document constitutes the agreement by the recipient that no unpublished information contained herein will be published or disclosed without prior written approval.

Secondary Assessments

Opioids (morphine equivalence) consumption within approx. first 30 postoperative days
 Postoperative pain self assessments
 CYP2B6*6 Genotype

Analysis

Sample Size: Our initial plan is to enroll ≥ 60 evaluable subjects in each of two cohorts for this pilot study. More specifically, this pilot plans 20 evaluable subjects in each methadone group within each cohort, with requisite proportional controls. Total number in each of the two cohorts will reflect the number of dose groups in each cohort (per escalation). Anticipated total evaluable is <200 .

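### The primary opioid total includes intraoperative opioid, which is assigned by arm, so it mixes the treatment with the response to it; the plan also leaves open what else Group I may receive in surgery

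*Combined protocol and SAP*

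**What the plan says.** **Outcome.** The Synopsis (Outcomes) lists "Primary: Intraoperative and postoperative opioid utilization". Section 9 (Primary Assessment) words it as "Overall opioid (morphine equivalents) consumption for each patient during hospital stay". Section 7 says the electronic record will be used to "calculate the amount of morphine or morphine equivalents administered during surgery and until discharge". All three include the intraoperative period. None says whether the study methadone is counted in the total, and no conversion factor to morphine equivalents is given.

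**Purpose.** The Abstract and section 2 (Background) frame the question as whether intraoperative methadone reduces opioid consumption after surgery. The Synopsis objective and Aim 1.1 also concern postoperative pain and opioid consumption.

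**Group I in surgery.** The Synopsis (Study Design) says "Subjects in Group I will receive methadone (IV bolus, at induction of anesthesia) as their primary intraoperative opioid". Section 6 says "subjects in methadone group will receive methadone as their intraoperative opioid, rather than leaving the choice of intraoperative opioid to the anesthesiologist". Section 2 says only that "Group I will receive a single dose of methadone during surgery". In control, the anesthesiologist chooses a non-methadone opioid, typically fentanyl or morphine.

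**Escalation.** Section 6 ties dose increases to postoperative need: "If patients still have significant post-op opioid requirements, subsequent groups may receive 0.2 mg/kg and then 0.3 mg/kg ideal body weight".

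**The concern.** A primary outcome should measure what happens as a result of the assigned treatment. Here one component of the total is the assigned treatment itself. Control patients receive fentanyl or morphine in surgery because they were randomized to it, and Group I patients receive methadone in its place for the same reason. A difference in the intraoperative part shows substitution of one opioid for another, not sparing.

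The regimen wording adds to this. If Group I may receive no other opioid in surgery, its non-methadone intraoperative amount is zero by design. If supplements are allowed, that amount depends on the judgment of the treating anesthesiologist, who can be expected to know the arm because the arm determines who chooses the opioid. Two anesthesiologists relying on different sections could deliver different regimens within Group I, and both would feed into the primary total.

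At stake is whether a reported reduction in opioid use can be read as a postoperative effect of methadone, which is the question the trial poses.

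**Working it through.** The plan states no expected opioid amounts, standard deviation, significance level or power, so there is no figure of its own to reproduce. The check is a comparison of the text, followed by simple algebra.

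**Step 1. The texts side by side.**

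| Place | What it fixes | What it leaves open |
|---|---|---|
| Synopsis, Study Design | Methadone is Group I's primary intraoperative opioid | Whether others may be added |
| Section 6 | Methadone replaces the anesthesiologist's choice | Whether it is the only opioid; no ban on additions is stated |
| Section 2 | One dose of methadone | Any other intraoperative opioid |
| Sections 7 and 9; Synopsis, Outcomes | Intraoperative opioid is in the primary total | Whether the methadone bolus is counted |

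**Step 2. What the total measures when methadone has no postoperative effect.** Set the control mean total to 1. Let
- *f* = intraoperative share of the control total,
- *s* = non-methadone opioid given to Group I in surgery, as a fraction of control intraoperative use,
- *b* = methadone bolus in morphine equivalents on the same scale (0 if not counted).

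Control total = *f* + (1 − *f*) = 1. Group I total = *b* + *s·f* + (1 − *f*).

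Control minus Group I = *f*(1 − *s*) − *b*.

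None of *f*, *s* and *b* is given in the documents. The sign depends on them:
- *f* = 0.3, *s* = 0, *b* = 0: difference 0.30 in favor of methadone.
- *f* = 0.3, *s* = 1, *b* = 0: difference 0.
- *f* = 0.3, *s* = 0, *b* = 0.3: difference 0.
- *f* = 0.3, *s* = 0, *b* = 0.45: difference −0.15, against methadone.

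If the bolus is counted with a fixed conversion factor, *b* at 0.3 mg/kg is 0.3/0.1 = 3 times *b* at 0.1 mg/kg. Higher dose levels would then start at a growing disadvantage on the total, whatever happens after surgery.

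**Step 3. Illustration of one scenario: bolus not counted.** Assumptions: 60 subjects at 1:2, so 20 control and 40 methadone, with dose levels pooled; one SD for both arms; two-sided 5% t-test with 58 df; no true postoperative effect.

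SE = SD × √(1/20 + 1/40), which is 0.137 for SD 0.5 and 0.219 for SD 0.8. The noncentrality is *f*(1 − *s*)/SE.

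| SD (share of control mean) | *s* | *f* | Difference | Noncentrality | Rejection probability |
|---|---|---|---|---|---|
| 0.5 | 0 | 0.3 | 0.30 | 2.19 | 0.58 |
| 0.5 | 0 | 0.6 | 0.60 | 4.38 | 0.99 |
| 0.8 | 0 | 0.3 | 0.30 | 1.37 | 0.27 |
| 0.8 | 0 | 0.6 | 0.60 | 2.74 | 0.77 |
| 0.5 | 0.5 | 0.3 | 0.15 | 1.10 | 0.19 |
| 0.5 | 0.5 | 0.6 | 0.30 | 2.19 | 0.58 |
| 0.5 or 0.8 | 1 | 0.3 or 0.6 | 0 | 0 | 0.05 |

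The table shows the mechanism in one scenario. It does not forecast its size in this trial.

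**Step 4. Effect of restricting the window.** Methadone is given at induction. Counting opioid only from the end of surgery removes *b* and *s·f* from Group I's total and *f* from control's, so the built-in difference is 0 for every value of *f*, *s* and *b*.

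**The case against.** **The two wordings do not conflict.** Neither the Synopsis nor section 6 expressly allows or forbids a second opioid. Section 6 can be read as settling who chooses the assigned opioid, and the word primary as naming the main one. This stands. A reader might infer that the protocol prescribes two incompatible regimens for Group I, but the text does not support that. It shows a question left unanswered, and alone that would be a matter of missing detail.

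**No section leaves the bolus out.** On their plain wording, sections 7 and 9 could include it, and the apparent saving would then shrink, vanish or reverse. This also stands. It is why the rejection probabilities are only an illustration, and why a near-certain false positive cannot be claimed. The probabilities also assume equal SDs, and they pool 40 methadone subjects where section 9 plans 20 per dose group. But the objection confirms the main point: the direction of the contrast depends on a counting choice that the plan does not make.

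**Intraoperative use was included on purpose.** Section 2 does propose to evaluate both periods. Both can still be reported. What does not follow is that their sum tests an effect on postoperative consumption.

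**Escalation.** A reader might infer that supplements would distort the dose decisions. Opioid added in surgery could lower early postoperative need, but the documents contain nothing to show that it would change a decision, so this is only a reason to display the data.

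**Conclusion.** The point holds in this form: the primary opioid total includes an intraoperative component that is part of the assigned treatment, while the stated purpose concerns opioid use after surgery. With no postoperative effect, the arm difference is *f*(1 − *s*) − *b*, and the plan fixes none of these quantities. That conclusion rests on the text and the algebra, not on assumed values.

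The size cannot be determined from the documents. With the bolus uncounted, no supplements, and an assumed intraoperative share of 30% to 60%, the built-in reduction is 30% to 60%. With full supplementation it is zero, and with the bolus counted it may reverse.

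The Group I wording is an unresolved ambiguity that adds to the problem. It is not a flat contradiction. The outcome definition should be changed before analysis, and the change is small.

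**What to change.** 1. Define the between-arm primary test as morphine equivalents given from the end of surgery until discharge, with one named timestamp in the electronic record marking the start. Align the Synopsis (Outcomes), section 7 and section 9 to this definition.
2. Report intraoperative non-methadone opioid separately, by arm and dose level, as a description of treatment received. Show it beside postoperative need at each escalation review.
3. If a whole-stay total is still reported, label it descriptive and state whether the methadone bolus is included and by what conversion.
4. Reconcile the Synopsis (Study Design) with section 6 so that one statement says whether Group I may receive non-methadone opioid during surgery. Which rule stands is for the investigators to decide.

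The cost is protocol wording and one split of data already to be taken from the electronic record. The downside is that the headline opioid-sparing figure may be smaller. One limit remains: opioid added in surgery can still influence early postoperative need, and item 2 makes that visible without removing it.

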Protocol p. 12, deleted sentence stating analysis to include total of “120 evaluable”

Abstract

The μ -opioid receptor agonist methadone is frequently used in adult anesthesia and adult pain therapy. Methadone has an extremely long half-life, which confers therapeutic advantage by providing more stable plasma concentrations and long-lasting pain relief. Methadone perioperative pharmacokinetics and effectiveness in perioperative pain relief in inpatients is well characterized. There is, however, no information on methadone use in an ambulatory surgery setting and outpatient procedures. This pilot investigation will determine effectiveness of intraoperative methadone in reducing postoperative opioid consumption and providing improved pain relief in patients undergoing moderately painful, ambulatory surgical procedures.

SYNOPSIS

Study Title	Methadone in Ambulatory Surgery
Objective	Two arm randomized controlled pilot study to evaluate the efficacy of a single dose of intraoperative methadone in reducing post-operative pain and opioid consumption in patients undergoing moderately painful, ambulatory (less than 24 hr hospital stay) surgical procedures. Our secondary goal is to assess opioid consumption and pain relief within the first 30 postoperative days
Study Period	Planned enrollment duration: Approximately 12 months. Planned study duration: Approximately 30 days per subject
Number of Patients	200 evaluable subjects
Study Medication Administration	At least 60 evaluable patients in each of two cohorts (ambulatory with less than 24 hr overnight stay, and same-day outpatients) will be randomized into two groups. Group I will receive 0.1- 0.3 mg/kg IV methadone HCl. Group II will be the control group and not receive any methadone.

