Inadequate pain relief has a significant psychological and physiological impact on patients. The degree to which postoperative pain is controlled impacts the ability of patients to cope with the next pain episode (1, 2). Postoperative pain itself is a risk factor for development of chronic pain syndromes (3).

Methadone is a μ opioid agonist which is highly efficacious in the treatment of acute, chronic, neuropathic and cancer pain. In adults it is increasingly being used as a first-line analgesic. Methadone is highly efficacious in adult anesthesia and postoperative pain (4, 5). The typical dose for adult inpatient anesthesia is 20 mg (nominally 0.3 mg/kg) at the beginning of anesthesia. Methadone is advantageous because it has slow elimination, resulting in prolonged effect and significantly diminished need for postoperative analgesics. Reducing postop opioid analgesic use also decreases the potential for opioid-related side effects. Methadone has a long half-life, averaging 24-36 hours in healthy adults and adolescent patients. It has no active metabolites or pro-drug forms. Methadone is metabolized in the liver primarily by cytochrome P450 CYP2B6 (6, 7).

Perioperative analgesia remains a major challenge for physicians who care for patients undergoing any type of surgery, including ambulatory and 24 hour observation procedures. We propose to compare the standard of care intraoperative opioid administration to intraoperative methadone bolus in reducing postoperative opioid consumption and prescribing.

Evaluating the role of methadone in ambulatory surgery patients is advantageous because 1) prolonged analgesia from methadone is expected to decrease the need for additional opioids in the immediate postoperative period, 2) opioid quantities routinely prescribed upon discharge may be reduced with methadone use, 3) lower overall dose of opioids administered can decrease possible side effects of opioids, and 4) improved immediate postoperative pain relief can decrease occurrence of chronic postoperative pain.

Assessment of pain has become standard practice in the treatment of surgical patients. Several tools are often used, including the Numeric Rating Scale and colored-visual analogue scale (8, 9, 10).

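### As written, the primary opioid total does not exclude the randomized methadone bolus and gives no conversion factor, so the assigned treatment enters its own outcome

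*Combined protocol and SAP*

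**What the plan says.** Four statements set the opioid outcome, and all of them take in the operation itself.

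- Synopsis, Outcomes: "Primary: Intraoperative and postoperative opioid utilization".
- Synopsis, Measurements: "Total intraoperative and postoperative opioid administration during hospitalization will be recorded".
- Section 7, Opioid Consumption During Hospitalization: "The EMR will be used to calculate the amount of morphine or morphine equivalents administered during surgery and until discharge".
- Section 9, Primary Assessment: "Overall opioid (morphine equivalents) consumption for each patient during hospital stay".

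The Synopsis (Study Design) places the randomized treatment in that span: "Subjects in Group I will receive methadone (IV bolus, at induction of anesthesia) as their primary intraoperative opioid". Control patients receive a non-methadone opioid in the same phase, chosen by the anesthesiologist. No section says whether the methadone bolus is counted, and none gives a conversion factor for methadone or any other opioid.

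The purpose is put in narrower terms elsewhere. Abstract: "This pilot investigation will determine effectiveness of intraoperative methadone in reducing postoperative opioid consumption". Section 2: "We propose to compare the standard of care intraoperative opioid administration to intraoperative methadone bolus in reducing postoperative opioid consumption and prescribing". The condition for raising the dose in Section 6 also looks only at the period after surgery: "If patients still have significant post-op opioid requirements". Sections 2 and 11 do mention a lower overall opioid dose as a possible benefit, and Section 2 proposes to evaluate intraoperative opioid as well.

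**The concern.** Taken literally, the primary variable adds to every Group I patient an amount fixed by randomization, dose level and ideal body weight, multiplied by a factor the plan does not state. Three things follow.

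- The size of the comparison, and possibly its sign, depends on that factor.
- Each dose step raises the Group I total by construction, so a higher dose can look worse even when patients need less opioid afterwards. Section 9 compares two groups; if dose levels are combined, the Group I mean also depends on the mix of doses.
- With no rule in place, whether to count the bolus, and at what factor, can be settled after data are seen. The trial is single blinded, and the Synopsis provides for a preliminary analysis of the initial Group I subjects.

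Leaving out the study dose alone does not repair this. Control intraoperative opioid would stay in the total while its Group I counterpart was removed.

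**Working it through.** **The plan's own figures.** No expected value, SD or effect size is given for this outcome. The sample size is a head count: 20 methadone subjects and, at 1:2, 10 controls per dose level. Two levels give 40 + 20 = 60 per cohort. Three give 60 + 30 = 90 per cohort, or 180 in all, below the 200 stated. This reproduces, and the present point does not affect it.

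**Inputs from the plan.** Doses of 0.1 to 0.3 mg/kg (Synopsis, Section 6). Section 2 equates 20 mg with a nominal 0.3 mg/kg, so the implied weight is 20 / 0.3 = 66.7 kg.

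**Assumed inputs (none in the documents).** Factor f = 1 to 3 mg morphine per mg methadone. Control: C = 15 mg intraoperative and 15 mg postoperative. Group I: 7.5 mg postoperative and S = 0 mg supplemental intraoperative opioid. The postoperative reduction is therefore 15 − 7.5 = 7.5 mg.

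**Step 1: what the bolus adds.** Bolus b = dose × 66.7 kg; contribution = f × b.

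| Dose (mg/kg) | b (mg) | f = 1 | f = 2 | f = 3 |
|---|---|---|---|---|
| 0.1 | 6.7 | 6.7 | 13.3 | 20 |
| 0.2 | 13.3 | 13.3 | 26.7 | 40 |
| 0.3 | 20 | 20 | 40 | 60 |

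**Step 2: the reduction as measured, with the bolus counted.** Reduction = (15 + 15) − (7.5 + f × b) = 22.5 − f × b. A negative value means methadone appears worse.

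| Dose (mg/kg) | f = 1 | f = 2 | f = 3 |
|---|---|---|---|
| 0.1 | +15.8 | +9.2 | +2.5 |
| 0.2 | +9.2 | −4.2 | −17.5 |
| 0.3 | +2.5 | −17.5 | −37.5 |

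The postoperative reduction is 7.5 mg in every cell.

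**Step 3: the factor at which the sign reverses.** f* = (C + 15 − 7.5 − S) / b.

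| Setting | 0.1 mg/kg | 0.2 mg/kg | 0.3 mg/kg |
|---|---|---|---|
| Base case | 3.375 | 1.69 | 1.125 |
| Weight 50 kg | 4.5 | 2.25 | 1.5 |
| Weight 80 kg | 2.8 | 1.4 | 0.94 |
| C = 10 mg | 2.6 | 1.3 | 0.88 |
| C = 20 mg | 4.1 | 2.1 | 1.4 |
| S = 5 mg | 2.6 | 1.3 | 0.88 |

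At 0.2 and 0.3 mg/kg, reversal occurs for some factor between 1 and 3 in every setting; where f* is below 1, the sign is reversed over the whole range. At 0.1 mg/kg the base case does not reverse, but three of the five variations do.

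**Step 4: dropping only the study dose.** With no postoperative effect at all, the measured difference is C − S. For C of 10 to 20 mg and S of 0 to 10 mg, it runs from 10 − 10 = 0 to 20 − 0 = 20 mg in favour of methadone.

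**The case against.** The best defence is that total opioid is a deliberate and coherent target. The outcome statements agree on it, Sections 2 and 11 give a reason for it, and each arm's own intraoperative opioid enters on the same terms. Methadone given is opioid received, and a rising total with rising dose is what such a measure should show. The illustration calls a changed sign an error only because it takes postoperative need as the target.

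That makes total exposure a legitimate second question. It does not make it the question in the Abstract, the Section 2 comparison or the Section 6 escalation condition. Even as a total, it cannot be computed without conversion factors.

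Other points on that side:

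- *The plan is silent rather than explicit about counting the bolus.* True, which is why the finding is confined to the wording. Neither reading of the total isolates postoperative need.
- *The amounts and factors are assumed.* True. At a factor of 0.5 the base case never reverses, but the measured reductions are 22.5 − 3.3 = 19.2, 22.5 − 6.7 = 15.8 and 22.5 − 10 = 12.5 mg against 7.5 mg. The two higher dose levels, where base-case reversal occurs, are also conditional.
- *Factors are missing for every opioid, not only methadone.* This stands and widens the remedy.
- *It is a pilot, and Section 9 also lists pain and sedation scores as primary.* Opioid use is nevertheless the only primary outcome in the Synopsis, and a between-group test of it is planned.
- *Changing a primary outcome at version 4.0 could itself be influenced by data.* This stands as a caution on how the change is documented.

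**Conclusion.** The concern holds. The stated span includes the randomized bolus, nothing excludes it, and no factor is given. Counting it adds an amount determined by assignment: 6.7 to 20, 13.3 to 40 or 20 to 60 mg morphine equivalents at 0.1, 0.2 or 0.3 mg/kg. In the base illustration, one and the same 7.5 mg postoperative saving is measured as anything from +15.8 to −37.5 mg. Removing only the study dose can instead create up to 20 mg of spurious benefit.

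The weight comes from the plan's own dose equivalence; the factors and opioid amounts are assumptions. The conclusion needs none of them to be exact, only that the result depends on a factor and an inclusion rule that are not stated. Because this affects the Synopsis's sole primary outcome and possibly its sign, it must be fixed before analysis.

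**What to change.** In the Synopsis and Sections 7 and 9:

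1. Define the primary opioid outcome as postoperative opioid in morphine equivalents from PACU arrival to discharge, excluding the study dose.
2. Report intraoperative opioid, and total perioperative exposure including methadone, separately as secondary or descriptive measures.
3. Prespecify a conversion table covering every opioid used, including fentanyl, with a sensitivity range for the methadone factor.
4. Optionally, add a sensitivity analysis over a fixed 24 h postoperative window, combining the EMR with the home diary.

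The amendment should be dated and should say whether the preliminary review of Group I had taken place and what had been seen, so that the change can be judged as following from the stated objective.

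The cost is wording. Intraoperative and postoperative opioid are already to be recorded from the EMR, and no procedure or sample size changes. What is given up is a primary measure that summarizes total exposure; it remains available as a secondary one.
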